8.3.7 Renal and Urological Safety Procedures

Safety assessments will be performed in all participants in order to monitor renal and urological safety during the course of the study. Participants will be monitored for hematuria using urinary dipstick (performed at the study site) and urinary crystals through urinalysis (performed at the central laboratory). Dipstick and urinalyses (including microscopy performed at the central laboratory) will be collected as outlined in the SoA.

If during screening, a participant has crystalluria and/or unexplained hematuria (defined as participants without a history of recent menses, urinary tract infection, or recent procedure/instrumentation that would explain the hematuria), the investigator should:

- Review and confirm if the finding is a new finding or a previously documented finding.
- Evaluate the participant's medical history to identify conditions (ie, prior renal disease, prior history of kidney stones, medications, gastrointestinal conditions) and make a clinical determination if the participant is at high or low risk of potential complications/worsening due to an associated renal/urinary condition or its treatment, or requires a change in therapy for that condition that may interfere with interpretation of safety data collected during the study.

- If high risk, the participant should not be enrolled and should be considered for further evaluation.
- If low risk, the participant may continue with screening.

If after randomization, the participant has confirmed, unexplained hematuria and/or urinary crystals, an urine sample collected via a specialized filter will be shipped to Sponsor or designee and assessed for the presence of MK-7264 urinary crystals via Raman spectroscopy. Raman spectroscopy is sensitive to the chemical structure of the molecule and MK-7264 has unique chemical structure compared to common urinary crystals. See vendor's site manual for further procedural details.

If a participant has confirmed MK-7264 urinary crystals, the Sponsor will inform the investigator and require discontinuation of the participant from study intervention with the recommendation to follow-up at approximately 2-week intervals with additional specialized urine analysis performed until resolution of MK-7264 urinary crystals.

8.4 Adverse Events (AEs), Serious Adverse Events (SAEs), and Other Reportable Safety Events

The definitions of an AE or SAE, as well as the method of recording, evaluating, and assessing causality of AE and SAE and the procedures for completing and transmitting AE, SAE, and other reportable safety event reports can be found in Appendix 3.

Adverse events, SAEs, and other reportable safety events will be reported by the participant (or, when appropriate, by a caregiver or surrogate).

The investigator, who is a qualified physician, is responsible for detecting, assessing, documenting, and reporting events that meet the definition of an AE or SAE, as well as other reportable safety events. Investigators remain responsible for following up AE, SAEs, and other reportable safety events for outcome according to Section 8.4.3.

8.4.1 Time Period and Frequency for Collecting AE, SAE, and Other Reportable Safety Event Information

All AEs, SAEs, and other reportable safety events that occur after the consent form is signed but before treatment allocation/randomization must be reported by the investigator if the participant is receiving placebo run-in or other run-in treatment, if the event cause the participant to be excluded from the study, or is the result of a protocol-specified intervention, including but not limited to washout or discontinuation of usual therapy, diet, or a procedure.

From the time of treatment allocation/randomization through last study-related intervention safety follow-up phone call, all AEs, SAEs and other reportable safety events must be reported by the investigator; however, for those participants who discontinue from the study intervention but continue to be monitored, only the AEs and other reportable safety events that are shown in [Table 3](#) need to be reported. This specific approach for reporting

starts from completion of the safety follow-up phone call/visit following cessation of intervention until the last study-related off-intervention phone call/visit.

Additionally, any SAE brought to the attention of an investigator at any time outside of the time period specified in the previous paragraph must be reported immediately to the Sponsor if the event is considered drug-related.

Investigators are not obligated to actively seek AE or SAE or other reportable safety events in former study participants. However, if the investigator learns of any SAE, including a death, at any time after a participant has been discharged from the study, and he/she considers the event to be reasonably related to the study intervention or study participation, the investigator must promptly notify the Sponsor.

All initial and follow-up AEs, SAEs, and other reportable safety events will be recorded and reported to the Sponsor or designee within the time frames as indicated in [Table 3](#).

Table 3 Reporting Time Periods and Time Frames for Adverse Events and Other Reportable Safety Events

Type of Event	Reporting Time Period: Consent to Randomization/ Allocation	Reporting Time Period: Randomization/ Allocation through Protocol-Specified Follow-up Period	Reporting Time Period: After the Protocol Specified Follow-up Period	Timeframe to Report Event and Follow-up Information to SPONSOR:
Non-Serious Adverse Event (NSAE)	Report if: - due to protocol-specified intervention - causes exclusion - participant is receiving placebo run-in or other run-in treatment	Report all	Not required	Per data entry guidelines
Serious Adverse Event (SAE)	Report if: - due to protocol-specified intervention - causes exclusion - participant is receiving placebo run-in or other run-in treatment	Report all	Report if: - drug/vaccine related. (Follow ongoing to outcome)	Within 24 hours of learning of event
Pregnancy/Lactation Exposure	Report if: - due to intervention - causes exclusion	Report all*	Previously reported – Follow to completion/termination; report outcome	Within 24 hours of learning of event

Type of Event	Reporting Time Period: Consent to Randomization/ Allocation	Reporting Time Period: Randomization/ Allocation through Protocol-Specified Follow-up Period	Reporting Time Period: After the Protocol Specified Follow-up Period	Timeframe to Report Event and Follow-up Information to SPONSOR:
Event of Clinical Interest (require regulatory reporting)	Report if: - due to intervention - causes exclusion	Report* - Potential DILI - Require regulatory reporting	Not required	Within 24 hours of learning of event
Event of Clinical Interest (Do not require regulatory reporting)	Report if: - due to intervention - causes exclusion	Report* - non-DILI ECIs and those not requiring regulatory reporting	Not required	Within 5 calendar days of learning of event
Cancer	Report if: - due to intervention - causes exclusion	Report all	Not required	Within 5 calendar days of learning of event
Overdose	Report if: - receiving placebo run-in or other run-in medication	Report all*	Not required	Within 5 calendar days of learning of event

* Participants who discontinue intervention and are continuing to be monitored in the study do not require the reporting of ECIs, Pregnancy/Lactation Exposure and Overdose. Previously reported pregnancies/lactation exposure need to be followed for completion/termination; report outcome.

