5.1 Inclusion Criteria

Participants are eligible to be included in the study only if all of the following criteria apply:

Type of Participant and Disease Characteristics

1. Chest radiograph or computed tomography scan of the thorax (within 5 years of Visit 1 and after the onset of chronic cough) not demonstrating any abnormality considered to be significantly contributing to the chronic cough or any other clinically significant lung disease in the opinion of the principal investigator or the sub-investigator.
2. Have cough for \geq 4 months at signing informed consent and a diagnosis of refractory or unexplained chronic cough as specified in Section 5.
3. The participant has persistent cough despite of treatment in accordance with the latest guideline of cough from the Japanese Respiratory Society and is burden to the participant and need further treatment in the opinion of the principal investigator or the sub-investigator.

Demographics

4. Participant is Japanese Male or Female from 20 years of age inclusive, at the time of signing the informed consent.

Female Participants

5. A female participant is eligible to participate if she is not pregnant (Appendix 5), not breastfeeding, and at least 1 of the following conditions applies:
 - a. Not a woman of childbearing potential (WOCBP) as defined in Appendix 5.

OR

- b. A WOCBP who agrees to follow the contraceptive guidance in Appendix 5 from signing informed consent to 14 days after the last dose of study intervention.

Informed Consent

6. The participant is able to provide written informed consent for the study on their own behalf. The participant may also provide consent for Future Biomedical Research. However the participant may participate in the main study without participating in Future Biomedical Research.

Study Participation

7. The participant is willing and able to comply with all aspects of the protocol including demonstrating an ability to follow study procedures (including completion of the patient report outcomes [PROs]) to the satisfaction of the investigator/qualified designee prior to randomization (see Section 8.1.2).

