8.3.6 Clinical Safety Laboratory Assessments

- Refer to Appendix 2 for the list of clinical laboratory tests to be performed and to the SoA for the timing and frequency.
- The investigator must review the laboratory report, document this review, and record any clinically relevant changes occurring during the study in the AE section of the case report form (CRF). The laboratory reports must be filed with the source documents. Clinically significant abnormal laboratory findings are those which are not associated with the underlying disease, unless judged by the investigator to be more severe than expected for the participant's condition.
- All protocol-required laboratory assessments, as defined in Appendix 2, must be conducted in accordance with the laboratory manual and the SoA.
- If laboratory values from nonprotocol specified laboratory assessments performed at the institution's local laboratory require a change in study participant management or are considered clinically significant by the investigator (eg, SAE or AE or dose modification), then the results must be recorded in the appropriate CRF (eg, SLAB).
- For any laboratory tests with values considered clinically significantly abnormal during participation in the study or within 14 days after the last dose of study intervention, every attempt should be made to perform repeat assessments until the values return to normal or baseline or if a new baseline is established as determined by the investigator.

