8.4.5 Pregnancy and Exposure During Breastfeeding

Although pregnancy and infant exposure during breastfeeding are not considered AEs, any pregnancy or infant exposure during breastfeeding in a participant (spontaneously reported to the investigator or their designee) that occurs during the study are reportable to the Sponsor.

All reported pregnancies must be followed to the completion/termination of the pregnancy. Pregnancy outcomes of spontaneous abortion, missed abortion, benign hydatidiform mole, blighted ovum, fetal death, intrauterine death, miscarriage, and stillbirth must be reported as serious events (Important Medical Events). If the pregnancy continues to term, the outcome (health of infant) must also be reported.

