8.10.6 Follow-up Period

All participants will be required to complete the safety follow-up telephone contact approximately 14 days (+7 days) after the last dose of study intervention to determine if any AEs have occurred since discontinuing study intervention.

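### The Table 3 footnote drops new pregnancy, lactation and ECI reports for off-drug participants still in the study, while Sections 8.4.5 and 8.4.7 require them without exception

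*Combined protocol and SAP*

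**What the plan says.** Section 8.4.1 of the protocol sets a full-reporting period that begins at randomization: "through last study-related intervention safety follow-up phone call, all AEs, SAEs and other reportable safety events must be reported". For participants who have stopped drug but are still followed, it then limits reporting to what Table 3 shows. It says this reduced scheme "starts from completion of the safety follow-up phone call/visit following cessation of intervention until the last study-related off-intervention phone call/visit". Section 8.10.6 places the call: all participants complete a "safety follow-up telephone contact approximately 14 days (+7 days) after the last dose of study intervention".

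The asterisked footnote to Table 3 reads: "Participants who discontinue intervention and are continuing to be monitored in the study do not require the reporting of ECIs, Pregnancy/Lactation Exposure and Overdose". It adds that pregnancies and lactation exposures already reported are still followed to outcome. It gives no start time.

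Two other sections cover the same events:

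- Section 8.4.5 says that a pregnancy or breastfeeding exposure "in a participant (spontaneously reported to the investigator or their designee) that occurs during the study are reportable to the Sponsor". It also says that pregnancy is not considered an AE.
- Section 8.4.7 requires ECIs to be reported. The one ECI listed is the combined transaminase and bilirubin criterion, whether met on protocol-specified or unscheduled testing.

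Neither section has an exception for participants off drug. Inclusion criterion 5b sets the contraception period "from signing informed consent to 14 days after the last dose of study intervention". For clinically significant laboratory abnormalities found during participation or within 14 days of last dose, Section 8.3.6 says that "every attempt should be made to perform repeat assessments until the values return to normal or baseline".

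**The concern.** A site with an off-drug participant who becomes pregnant meets two opposite instructions: Section 8.4.5 says report, and the Table 3 footnote says no report is needed. Sections 7.1 and 8.10.5 keep such participants in the study by design, so the pregnancy does occur during the study. Sites that follow different passages will report differently.

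Pregnancy is the harder case because it has no fallback. The AE and SAE rows of Table 3 carry no asterisk, but a pregnancy is not an AE and does not enter through them. The footnote preserves follow-up to outcome only for pregnancies already reported. A pregnancy conceived on drug and recognised late may therefore be neither reported nor followed, although the site is still in contact with the participant.

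For ECIs the issue is milder. A liver abnormality found on treatment may be retested after the safety call under Section 8.3.6 and first meet the ECI criterion then. Under the footnote it would no longer be an ECI with a 24-hour report.

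**Working it through.** **1. How many participants could enter this status.** The plan (protocol Section 9.9) assumes about 47% discontinuation among 160. 160 × (1 − 0.47) = 84.8, which agrees with the stated 84 completers. 160 − 84 = 76 participants (76/160 = 47.5%) are expected to stop early. This counts everyone. The documents give no number of women of childbearing potential, so the pregnancy subset cannot be computed.

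**2. How long the reduced reporting can last.** The call falls 14 to 21 days after last dose, and Visit 8 is Day 365.

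- Stop on Day 28: call on Day 42 to 49, leaving 365 − 49 = 316 to 365 − 42 = 323 days.
- Stop on Day 168: call on Day 182 to 189, leaving 365 − 189 = 176 to 365 − 182 = 183 days.

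**3. Which conceptions are missed under the Section 8.4.1 timing.** After Visit 1, Appendix 5 calls for a pregnancy test only after a missed cycle or on suspicion, so a lag between conception and recognition has to be assumed. I take 14 to 28 days; this is not a figure from the documents. Count days from last dose (day 0).

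- Last covered conception day = day of call − lag.
- Uncovered part of the contraception window = 14 − last covered day.
- Uncovered on-drug days = 0 − last covered day, or zero if that is negative.

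| Call (day) | Lag (days) | Last covered conception day | Uncovered to day +14 | Of these, on drug |
|---|---|---|---|---|
| 14 | 14 | 0 | 14 | 0 |
| 14 | 28 | −14 | 28 | 14 |
| 21 | 14 | +7 | 7 | 0 |
| 21 | 28 | −7 | 21 | 7 |

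The range is 7 to 28 days of the contraception window, of which 0 to 14 days are on drug.

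**4. What happens to a liver case after the call.** Setting the passages together:

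- Section 8.4.7: an ECI, to be reported. Table 3 gives potential DILI a 24-hour timeline.
- Table 3 footnote: no ECI report for an off-drug monitored participant.
- Table 3 AE and SAE rows: all reportable through follow-up, with no asterisk. SAEs keep the 24-hour timeline; non-serious AEs follow the data entry guidelines.
- Appendix 3: abnormal laboratory results can qualify as AEs.
- Section 8.10.5: no laboratory tests are scheduled off drug after the Discontinuation Visit.

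So what lapses is the ECI category and the 24-hour timeline. It lapses only for non-serious cases that first meet the criterion on repeat or unscheduled tests after the call.

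**5. Effect on the primary summary.** Section 3.6.2 of the supplemental SAP counts AEs up to 14 days after last dose. The call is at or after that point, so the summary is little affected.

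**The case against.** The strongest reply is that Table 3 belongs to Section 8.4.1, which states when the reduced scheme starts. The footnote applies that sentence and does not contradict it. This stands. A reader of the footnote alone might infer that reporting stops on the day drug stops, so that an ECI on the Discontinuation Visit sample needs no report. The documents do not support that. Section 8.4.1 keeps full reporting through the safety call, and Section 8.10.5 wants that visit as soon as possible after stopping, so its sample normally falls inside the full-reporting period. The remaining fault is that the table sites consult for timing omits the start time.

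A second reply is that little is lost. Liver events stay reportable as AEs or SAEs, and drug-related SAEs are reportable at any time. Section 8.4.5 makes pregnancy losses serious events, and a congenital anomaly is an SAE. With a half-life of 7 to 10 hours (Section 4.3.3), 14 days is 14 × 24/10 = 33.6 to 14 × 24/7 = 48 half-lives, so conceptions late in the window carry little or no exposure. At a 14-day recognition lag no on-drug conception is missed. All of this is fair, and it limits the size of the problem. It does not supply a route for an exposed pregnancy recognised after the call, unless that pregnancy ends in an event reportable as serious.

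Third, a reader might extend the point to completers, since Table 3 follows only pregnancies already reported once the follow-up period is over. Section 8.4.5 covers pregnancies during the study, and a completer has then left it, so no passage is contradicted.

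**Conclusion.** The conflict is real but narrow. For off-drug participants still in the study, the Table 3 footnote removes reports that Section 8.4.5 requires for pregnancy and lactation exposure and that Section 8.4.7 requires for ECIs. The footnote also omits the start time given in Section 8.4.1.

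The consequence that matters is a pregnancy conceived on drug and recognised after the safety call. Up to 14 on-drug conception days are uncovered, or 7 to 28 days of the protocol's contraception window, if recognition takes 14 to 28 days. The low end of the on-drug range is zero, and the number of participants affected is unknown and may be small.

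It would be tempting to conclude that possible drug-induced liver injury goes unrecorded after a stop. The documents do not support that, because such cases remain reportable as AEs or SAEs. This is a wording reconciliation that the sponsor should make, held with moderate confidence. It does not threaten the primary analysis.

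**What to change.** Reconcile the Table 3 footnote with Sections 8.4.1, 8.4.5 and 8.4.7:

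- State in the footnote that the exemption starts on completion of the safety follow-up call, as Section 8.4.1 already provides.
- Keep reportable, and followed to outcome, any pregnancy in a monitored participant with estimated conception within the protocol's existing contraception window, that is, up to 14 days after last dose.
- Keep reportable as an ECI any case in which the criterion is reached on repeat testing of an abnormality first found on treatment or within 14 days of last dose.
- Align the wording of Sections 8.4.5 and 8.4.7 with the amended footnote, so that all the passages give a site the same answer.

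The cost is protocol wording and a line in the data entry guidelines. It adds no visits or tests. The downside is a few extra reports.

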8.4.2 Method of Detecting AEs, SAEs, and Other Reportable Safety Events

Care will be taken not to introduce bias when detecting AE and/or SAE and other reportable safety events. Open-ended and nonleading verbal questioning of the participant is the preferred method to inquire about AE occurrence.

8.4.3 Follow-up of AE, SAE, and Other Reportable Safety Event Information

After the initial AE/SAE report, the investigator is required to proactively follow each participant at subsequent visits/contacts. All AE, SAE, and other reportable safety events including pregnancy and exposure during breastfeeding, events of clinical interest (ECI), cancer, and overdose will be followed until resolution, stabilization, until the event is otherwise explained, or the participant is lost to follow-up (as defined in Section 7.3). In addition, the investigator will make every attempt to follow all nonserious AEs that occur in randomized participants for outcome. Further information on follow-up procedures is given in Appendix 3.

8.4.4 Regulatory Reporting Requirements for SAE

Prompt notification (within 24 hours) by the investigator to the Sponsor of SAE is essential so that legal obligations and ethical responsibilities towards the safety of participants and the safety of a study intervention under clinical investigation are met.

The Sponsor has a legal responsibility to notify both the local regulatory authority and other regulatory agencies about the safety of a study intervention under clinical investigation. All AEs will be reported to regulatory authorities, IRB/IECs, and investigators in accordance with all applicable global laws and regulations (ie, per ICH Topic E6 (R2) Guidelines for Good Clinical Practice [GCP]).

Investigator safety reports must be prepared for suspected unexpected serious adverse reactions (SUSARs) according to local regulatory requirements and Sponsor policy and forwarded to investigators as necessary.

An investigator who receives an investigator safety report describing an SAE or other specific safety information (eg, summary or listing of SAE) from the Sponsor will file it along with the IB and will notify the IRB/IEC, if appropriate according to local requirements.

8.4.5 Pregnancy and Exposure During Breastfeeding

Although pregnancy and infant exposure during breastfeeding are not considered AEs, any pregnancy or infant exposure during breastfeeding in a participant (spontaneously reported to the investigator or their designee) that occurs during the study are reportable to the Sponsor.

All reported pregnancies must be followed to the completion/termination of the pregnancy. Pregnancy outcomes of spontaneous abortion, missed abortion, benign hydatidiform mole, blighted ovum, fetal death, intrauterine death, miscarriage, and stillbirth must be reported as serious events (Important Medical Events). If the pregnancy continues to term, the outcome (health of infant) must also be reported.

